6.1.1 ADVERSE EVENT SEVERITY GRADES

The Investigator is responsible for evaluating all AEs and determining the severity of the event. Severity will be categorized according to the following definitions:

- Mild: Event may be noticeable to subject; does not influence daily activities; usually does not require intervention
- Moderate: Event may be of sufficient severity to make subject uncomfortable; performance of daily activities may be influenced; intervention may be needed
- Severe: Event may cause severe discomfort; usually interferes with daily activities; subject may not be able to continue in the study; treatment or other intervention usually needed

The Investigator will follow all subjects who experience AEs until there is a return to the subject's baseline condition or until a clinically satisfactory resolution is achieved or the subject is lost to follow-up.

6.1.2 INVESTIGATIONAL PRODUCT CAUSALITY

Relationship of an AE to investigational product will be assessed as follows:

- Definite: There is a clinically plausible time sequence between the onset of the AE and the application of investigational product; when the event responds to withdrawal of investigational product and recurs with re-administration of investigational product.
- Probable: There is a clinically plausible time sequence between the onset of the AE and the application of investigational product; the AE is unlikely to be caused by the concurrent/underlying illness, other drugs or procedures.
- Possible: There may or may not be a clinically plausible time sequence between the onset of the AE and the application of investigational product and a cause cannot be ruled out.
- Unlikely: There is no reasonable temporal association between the test material and the suspected event and the event could have been produced by the subject's clinical state or other modes of therapy administered to the Subject.
- Unrelated: This term should be reserved for those events that cannot be even remotely related to study participation.

6.2 REPORTING ADVERSE EVENTS

For the purpose of AE reporting the trial period is defined as the period after the subject signs the informed consent/assent to the end of subject's last visit.

The Investigator will assess subjects at each scheduled study visit for the occurrence of AEs. In order to avoid bias in eliciting AEs, subjects should be asked the following non-leading question: *“How have you felt since your last visit?”* All AEs (serious and non-serious) reported by the subject must be recorded on the subject's study record and entered into the study database.

In addition, QST must be notified within 24 hours of the Investigator's knowledge of the event by telephone or email of any immediately reportable events according to the procedure outlined below. Special attention should be paid to recording hospitalizations and concomitant therapies and medications.

6.3 IMMEDIATELY REPORTABLE EVENTS

Serious adverse events (SAEs) are considered immediately reportable events. Any SAE, whether deemed drug-related or not, must be reported to QST by telephone or email as soon as possible after the investigator or coordinator has become aware of its occurrence. The

investigator/coordinator must complete a Serious Adverse Event (SAE) Form and email it to QST along with the subject's Adverse Events Log and Concomitant Medications Log within 24 hours of notification of the event. When appropriate, Novan will notify the appropriate regulatory body of drug related Serious Adverse Events.

Serious Adverse Event (SAE) and Safety Contact Information:

Email: [contact]

If a subject experiences an SAE or pregnancy the Investigator must:

1. Report the SAE or pregnancy by telephone or email immediately (within 24 hours) after the Investigator becomes aware of the event.
2. Complete an SAE or Pregnancy Notification Form and email or overnight courier to QST within 24 hours of knowledge of the event.
3. Obtain and maintain all pertinent medical records, information and medical judgments of medical personnel who assisted in subject's treatment and follow-up and document as appropriate.
4. Provide a more detailed report to both QST and the IRB, if applicable, no later than seven days after the Investigator discovers the event as further information becomes available, and when necessary update the information with follow-up information including outcomes. This report should include a statement as to whether the event was or was not related to the use of investigational product.
5. The Investigator will notify the IRB of the SAE or pregnancy according to specific IRB requirements.

The Investigator will collect information on SAEs until the subject's health has returned to baseline status, until all parameters have returned to normal, or remaining health issues have otherwise been explained.

6.4 PREGNANCY

Women of child-bearing potential (WOCBP) must use an effective method of birth control during the course of the study and for 30 days following their final study visit. Allowable methods of birth control include stabilized oral contraceptive for at least three months, IUD, condom with spermicide, diaphragm with spermicide, implant, NuvaRing®, injection, transdermal patch or abstinence with a documented second acceptable method of birth control should the subject become sexually active. Females taking hormonal contraceptives must have taken the same type for at least three months (90 days) prior to entering the study and must not change type during the study. Those who have used birth control pills or hormonal contraception in the past and stopped must have discontinued usage at least three months prior to the start of the study.

A female is considered to be of childbearing potential unless she is post-menopausal (no menses for 24 consecutive months), surgically sterilized, or without a uterus and/or both ovaries.

Male subjects must agree to avoid fathering a child during the study and for 60 days after the last dose of study drug by ensuring one of the acceptable methods of contraception listed is used and by not donating sperm.

Before enrolling any subject in this clinical trial, the Investigator must review guidelines about study participation including the topics below:

- Informed consent document
- Pregnancy prevention information
- Risks to unborn child(ren)
- Any drug interactions with hormonal contraceptives
- Contraceptives in current use
- Guidelines for the follow-up of a reported pregnancy

Prior to study enrollment, all subjects must be advised of the importance of avoiding pregnancy during participation in this clinical study and the potential risk factors for an unintentional pregnancy. The subject must sign an informed consent document stating that the above-mentioned risk factors and the consequences were discussed.

During the study, WOCBP should be instructed to contact the Investigator immediately if they suspect they might be pregnant (e.g., missed or late menstrual cycle). Male subjects should be instructed to contact the investigator if their female partner becomes pregnant during the time the subject is enrolled through in the study through 60 days after the final visit. The Investigator must immediately notify QST of any female subject or the female partner of a male subject who becomes pregnant any time during study participation, record the information on the Pregnancy Notification Form and email the form to QST. Subjects found to be pregnant prior to Week 12 will be discontinued from the study. QST will ask the site to follow-up with the subject periodically during the pregnancy for ongoing health and safety information through term, as applicable. Protocol-required procedures for the Week 12/ET evaluation must be performed for the subject.

6.5 FOLLOW-UP OF ADVERSE EVENTS

6.5.1 FOLLOW-UP OF NON-SERIOUS ADVERSE EVENTS

Non-serious AEs that are not resolved at the time of the last scheduled study visit (Week 12/ET) must be recorded in the study database as not recovered/not resolved.

6.5.2 FOLLOW-UP OF POST STUDY SERIOUS ADVERSE EVENTS

Serious adverse events that are identified on the last scheduled contact (Week 12/ET) must be recorded in the study database and reported to QST according to the reporting procedures outlined in Sections 6.2 and 6.3. This may include unresolved previously reported SAEs, or new SAEs. The Investigator should follow these SAEs until the events are resolved, or the subject is lost to follow-up. The Investigator should continue to report any significant follow-up information to QST and the IRB up to the point the event has been resolved. Resolution means the subject has returned to the baseline state of health, or the Investigator does not expect any further improvement or worsening of the subject's condition.

Any new SAEs reported by the subject to the Investigator that occur after the last scheduled contact and are determined by the Investigator to be reasonably associated with the application of investigational product should be reported to QST and the IRB.

6.6 OVERDOSAGE

There is no specific antidote for nitric oxide. In the event of an overdose, best supportive care should be utilized. Methylene blue may be used to treat subjects exhibiting methemoglobinemia (Boylston, 2002).

6.7 DISCONTINUATION OF INDIVIDUAL SUBJECTS FROM THE STUDY

Subjects who develop intolerance to the product as defined by scores of 'severe' (3) on 2 or more categories of tolerability (erythema, scaling, dryness, pruritus, burning/stinging) shall be discontinued from the study.

Subjects with > 5.0% methemoglobin at any post-baseline visit will be discontinued from the study.

If a subject is determined to be pregnant prior to Week 12, the subject will be discontinued from the study but followed until term.

7. STATISTICAL ANALYSIS

7.1 GENERAL CONSIDERATIONS

All statistical processing will be performed using SAS® version 9.3 unless otherwise stated. Statistical significance will be based on two-tailed tests of the null hypothesis resulting in p-values of ≤ 0.05 unless stated otherwise. Inferential testing will compare each active treatment group to the combined Vehicle treatment group. Comparisons will not be performed between active treatments. Efficacy analyses will be performed for the intent-to-treat (ITT) and per-protocol (PP) populations. Safety analyses will be performed using the safety population.

For the dichotomized IGA, subjects will be considered a success if their IGA score is clear or almost clear and at least two grades less than Baseline.

For those subjects for whom no Week 12 assessments are available, the last observation will be carried forward (LOCF) in order to provide a value for efficacy parameters that are missing, primarily due to missed visits. Additionally, a sensitivity analysis to estimate missing efficacy data will be based on estimation using the method of Markov Chain Monte Carlo (MCMC) independently for each treatment group. All hypotheses will be two-sided at an alpha level of 0.05.

A detailed description of the statistical methodology and data reporting for this study will be provided in the Statistical Analysis Plan (SAP). The SAP will be finalized before the database is locked and released to Novan. Any deviations from the SAP will be justified in the clinical study report.

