I agree to obtain formal written informed consent in accordance with applicable federal and local regulations and international guidelines from all subjects prior to their entry into the study.

I have received and reviewed the Investigator's Brochure including the potential risks and side effects of the product and instructions for use.

I agree to report to Novan, Inc. or designee adverse events that occur during the course of the study in accordance with the ICH GCP guideline and the protocol.

I agree to ensure that all associates, colleagues and employees assisting me with the conduct of the study are informed of their responsibilities in meeting the above commitments and the commitments set forth in this Investigator's Agreement.

I agree to maintain adequate and accurate records and to make those records available for inspection in accordance with the ICH GCP guideline, and federal and local requirements.

The Investigator, agreeing to be fully bound, hereby executes this agreement on the date as set forth below.

Investigator Signature

Printed Name

Date

Address

Phone Number

PROTOCOL SYNOPSIS

Name of Sponsor/Company: Novan, Inc.	Individual Study Table Referring to Part of the Dossier: Volume: Page:	(For National Authority Use Only)	
Name of Finished Product: SB204			
Name of Active Ingredient: NVN1000			
Title	A Phase 2, Multi-Center, Randomized, Evaluator-Blinded, Vehicle-Controlled Study Comparing the Efficacy, Tolerability, and Safety of SB204 Gel and Vehicle Gel Once or Twice Daily in the Treatment of Acne Vulgaris		
Study Objectives	The primary objective of this study is to compare the efficacy, tolerability, and safety of two concentrations of SB204 Gel and Vehicle Gel once or twice daily for 12 weeks in subjects with moderate to severe acne vulgaris on the face.		
Treatment Regimens	Eligible subjects at the Baseline visit will be randomized 2:2:2:1:1 to SB204 4% Gel BID, SB204 4% Gel QD, SB204 2% Gel BID, Vehicle Gel BID, or Vehicle Gel QD and treated for 12 weeks (84 days).		
Formulation	Investigational Drug: SB204 4% Gel Investigational Drug: SB204 2% Gel Comparator Drug: Vehicle Gel		
Study Period	Subjects will be dosed in the study for up to 12 weeks.		

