2.2 STUDY OBJECTIVES

The primary objective of this study is to compare efficacy, tolerability and safety of two concentrations of SB204 Gel and Vehicle Gel once or twice daily for 12 weeks in subjects with acne vulgaris.

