3.1.3 SAFETY ENDPOINTS

Safety endpoints will include the change from baseline in percent methemoglobin, change from baseline vital sign measurements and in chemistry, hematology, and PT/PTT values, and the comparison of adverse events between groups. Any clinically significant changes noted during the physical exam as well as from the vital sign measurements, or safety laboratory assessments will be recorded as adverse events and included in the comparison.

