7.4 DESCRIPTIVE STATISTICS

Descriptive statistics will be presented for the efficacy data at each evaluation for the ITT and PP populations. Safety data will be summarized as indicated below for the safety population.

Continuous data will be summarized with sample size (N), mean, median, standard deviation, minimum and maximum. Categorical data will be summarized with N, frequency counts, and percentages.

Descriptive statistics will be presented for the active treatment groups, each vehicle treatment group, and the vehicle treatment groups combined.

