7.7 SAFETY

7.7.1 ADVERSE EVENTS

All AEs that occur during the study will be recorded and classified on the basis of Medical Dictionary for Regulatory Activities (MedDRA) terminology. Treatment-emergent AEs (TEAEs) are defined as AEs with an onset on or after the date of the first study drug dose. Adverse events noted prior to the first study drug administration that worsen after Baseline will also be reported as AEs and included in the summaries.

All information pertaining to an AE noted during the study will be listed by subject, detailing verbatim term given by the PI or designee, preferred term, system organ class (SOC), onset date, resolution date, severity, seriousness, action taken, outcome, and drug relatedness. The event onset will also be shown relative (in number of days) to date of first dose.

Treatment-emergent AEs will be summarized by treatment group, the number of subjects reporting a TEAE, SOC, preferred term, severity, relationship to study drug (causality), and

seriousness. When summarizing AEs by severity and relationship, each subject will be counted only once within a system organ class or a preferred term by using the event with the highest severity and greatest relationship within each classification.

Serious AEs will be summarized by treatment group, severity, and relationship to study drug, and individual SAEs will be listed by subject. In addition, a list of subjects who prematurely discontinue from the study due to an AE will be provided.

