7.8 SAMPLE SIZE AND POWER CONSIDERATIONS

Approximately 200 subjects will be randomized into the study in a 2:2:2:1:1 ratio (~ 50 in each active arm and ~25 in each vehicle arm) at approximately 20 sites in North America. The main objective of this study is to evaluate the efficacy, tolerability and safety of SB204 with respect to vehicle.

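### Does the sentence ruling out comparisons between active treatments also shut out estimates of concentration and frequency differences?

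*Protocol*

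**What the plan says.** Section 7.1 and the Synopsis (Statistical Methods) carry the same two sentences in the same order. The first sets the scope of inference: "Inferential testing will compare each active treatment group to the combined Vehicle treatment group". The second follows at once: "Comparisons will not be performed between active treatments".

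The objective appears in three places. The Synopsis says the study is to "compare the efficacy, tolerability, and safety of two concentrations of SB204 Gel and Vehicle Gel once or twice daily", and Section 2.2 is to the same effect: "compare efficacy, tolerability and safety of two concentrations of SB204 Gel and Vehicle Gel once or twice daily". Section 7.8 puts it more narrowly: "The main objective of this study is to evaluate the efficacy, tolerability and safety of SB204 with respect to vehicle".

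For description, Section 7.4 plans that "Descriptive statistics will be presented for the active treatment groups, each vehicle treatment group, and the vehicle treatment groups combined". Continuous data get N, mean, median, SD and range; categorical data get counts and percentages. Section 7.5 applies this to lesion counts, their changes and dichotomized IGA through Week 12.

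On safety, Section 3.1.3 lists "the comparison of adverse events between groups" among the endpoints, and Section 7.7.1 delivers it as description: "Treatment-emergent AEs will be summarized by treatment group".

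**The concern.** The second sentence of the pair carries no qualifier. It does not say hypothesis tests; it says comparisons. Section 3.1.3 shows that the protocol can use that word for output with no test attached, since the adverse event comparison is carried out in Section 7.7.1 purely by summaries. On a literal reading, a statistical analysis plan that follows the protocol could not add even an exploratory, baseline-adjusted estimate with an interval for 4% BID against 2% BID, or for 4% BID against 4% QD.

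The objective sharpens the doubt. The Synopsis and Section 2.2 mention two concentrations and once or twice daily use, which can be taken as a promise to compare regimens with one another. If that were the aim, the analysis section would exclude part of the primary objective. A trial with three active regimens would then end with three p-values against one pooled vehicle group, and readers might rank the regimens by those p-values.

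**Working it through.** **Scope of the sentence**

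1. In Section 7.1 the sentence ends a run about testing: two-tailed tests and p-values, then which groups are tested, then which are not. In that position it is the negative half of the statement on inferential testing.
2. Section 7.5 uses the same vocabulary for inference. Its pairwise comparisons are each active arm against combined vehicle, and it says they are not adjusted for multiplicity, a remark that has meaning only for inference. The verb is used again for the log-rank test of time to improvement.
3. If the word also covered descriptive contrasts, Section 7.1 would conflict with Section 3.1.3, which compares adverse events across groups without limiting this to active against vehicle. Read as a bar on inferential testing, Sections 3.1.3, 7.1, 7.4, 7.5 and 7.7.1 all agree.
4. The objective in the Synopsis and Section 2.2 names SB204 at two concentrations and vehicle. Its ordinary meaning is SB204 regimens against vehicle, as in the trial's title, and Section 7.8 says this outright.

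**What would be lost on the strictest reading**

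Arm sizes (Section 7.8): 200 × 2/8 = 50 per active arm and 200 × 1/8 = 25 per vehicle arm, as the protocol states.

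Unadjusted difference between two active arms, in SD of change:
- SE = √(1/50 + 1/50) = 0.200
- 95% half-width = 1.96 × 0.200 = 0.392

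A planned contrast with combined vehicle is 50 against 25 + 25, so it has the same precision. The N, mean and SD promised in Section 7.4 are enough for any reader to form the difference and its interval.

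Gain from the planned ANCOVA: with r the baseline to Week 12 correlation and k the ratio of baseline SD to Week 12 SD, the adjusted half-width divided by the unadjusted one is √[(1 − r²)/(1 + k² − 2rk)]. The protocol gives neither r nor k, so both are assumed.

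| k | r = 0.3 | r = 0.5 | r = 0.7 |
|---|---|---|---|
| 1.0 | 0.806 | 0.866 | 0.922 |
| 0.75 | 0.904 | 0.961 | 0.998 |
| 0.5 | 0.979 | 1.000 | 0.963 |

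The adjusted half-width therefore runs from 0.392 × 0.806 = 0.316 to 0.392 × 1.000 = 0.392, which is 0% to 19% narrower. The 19% needs k = 1 and r = 0.3. Entry limits truncate baseline counts (20 to 40 inflammatory, 25 to 70 non-inflammatory; Section 3.7.2) and nothing bounds Week 12 counts in that way, so k below 1 is plausible, though not shown. The gain is then at most about 10% at k = 0.75 and 4% at k = 0.5.

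IGA success: the Cochran-Mantel-Haenszel test provides no covariate-adjusted model, so no adjusted estimate is lost. A risk difference follows from the planned counts, with half-width 1.96 × √[2p(1 − p)/50]. At assumed success rates of 10%, 20%, 30% and 40% in both arms this is 0.118, 0.157, 0.180 and 0.192, or about 12, 16, 18 and 19 percentage points.

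**The case for a change.** The best case for the concern is that this is a restriction stated by the protocol itself, so it cannot be dismissed as detail left to the statistical analysis plan. The drafters moved from inferential testing in one sentence to comparisons in the next, and someone writing the analysis plan might take the change as deliberate. A contrast between active arms would be as precise as the planned ones, would cost no subjects and no alpha, and would tell readers more than ranking p-values against a shared control.

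Part of this stands. The sentence has no qualifier, and naming hypothesis tests would be tidier. But that edit changes no result, because the context already supplies the meaning.

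Adding the estimates is a different matter. Two contrasts on three co-primary endpoints make 2 × 3 = 6 further intervals, in a protocol that already sets multiplicity control aside. A 95% interval that excludes zero will be read as a test at 0.05, which is what the sponsor chose not to do. The 4% BID against 4% QD contrast also changes the daily amount, so it does not isolate frequency. A statistician could reasonably prefer to have these intervals, but that is a preference about design and not the correction of an error.

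**Conclusion.** The concern does not stand. In its place in Section 7.1 and the Synopsis, the sentence limits inferential testing to each active regimen against combined vehicle. That agrees with the pairwise analyses in Section 7.5 and the objective in Section 7.8, and the objective wording in the Synopsis and Section 2.2 fits it on its ordinary reading. There is no contradiction, no biased result and no change to the primary analysis.

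If the sentence were nevertheless applied to estimates, the loss would be a narrowing of 0% to 19% in intervals for lesion counts (half-width 0.32 to 0.39 SD of change), and no adjusted estimate would be lost for IGA. This rests on about 50 subjects per active arm with no allowance for dropout, an assumed r of 0.3 to 0.7 and an assumed k of 0.5 to 1.0. The statistical analysis plan was not available. The conclusion does not depend on what it adds, because the protocol's own per-arm summaries already support the unadjusted differences.
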